### 4.3. Secondary Endpoint(s) Analyses

#### 4.3.1. Definition of secondary endpoint(s)

Safety Endpoints

 
Incidence of SAEs, Deaths and AEs leading to Discontinuation through Day 8
 

PK Endpoints

Following QD dosing:
 
 
Day 1: Cmax, tmax, C24 and AUC(0-24)
 
Day 7: Cmax, tmax, C24 and AUC(0-24)
 

Following single dose: Cmax, tmax, AUC(0-168) and C168

For definition of secondary estimands see Section 1.1.1.

#### **4.3.1.1. Main analytical approach**

All secondary Safety and PK analyses will be performed on the Safety and PK analysis set, respectively.

#### **4.3.1.2. Adverse Events analyses**

AEs will be coded to the preferred term (PT) level using the Medical Dictionary for Regulatory Affairs (MedDRA) using the latest version at time of database release. AEs will be graded by the investigator according to the Division of AIDS (DAIDS) Criteria Version 2.1.

The number and percentage of participants reporting AEs during the treatment period will be summarised using the following categories and subcategories:

- AEs
  - By System Organ Class and Maximum Grade
- AEs leading to permanent discontinuation of study treatment
- Drug-related AEs
  - Overall
  - By Maximum Grade
- Drug-related Non-serious AEs
- Non-Serious AEs
- SAEs by System Organ Class and Maximum Grade
- Drug-related SAEs

The non-Serious AEs display will also include the number of events of an AE.

Selected displays from the above list will be repeated for AEs with onset during the Follow-Up period and during either the monotherapy or the Follow-Up period. AEs with onset in the treatment period which continue in the Follow-Up period will only be included in AE summaries for the treatment period. See OPS for the exact AE tables to be repeated for Follow-Up and monotherapy + Follow-Up.

A listing of all AEs and a listing of reasons for considering as SAE will be provided.

All planned AE displays are provided in the OPS document.

#### **4.3.1.3. Pharmacokinetic Analyses**

Pharmacokinetic parameters for VH3739937 will be calculated by standard non-compartmental analysis according to current working practices and using the currently supported version of WinNonlin. All calculations of non-compartmental parameters for the End of Study analysis will be based on actual sampling times. For the calculation of the Area under the concentration-time curve (AUC), the linear trapezoidal method will be employed for all incremental trapezoids arising from increasing concentrations and the logarithmic trapezoidal method will be used for those arising from decreasing concentrations (i.e., Linear Up/Log Down calculation method in Phoenix WinNonlin

Professional). A minimum number of three data points (not including Cmax) should be used in calculating  $\lambda z$ .

The adjusted correlation coefficient (R2 adjusted) should be greater than or equal to 0.80. Any value <0.80 should be considered for exclusion from descriptive summary. All derived parameters (half-life, AUC0-inf, CL, V) will need to be flagged or excluded from statistical analysis but will be included in individual listings. The percent of AUC0-inf extrapolated (%AUCextrap) should not exceed more than 20%. Subject's AUC0-inf parameter with %AUCextrap >20% will be flagged and excluded from statistical analysis but will be included in individual listings.

**Table 2      Definition of PK parameters**

PK Parameter	Definition
C max	Maximum observed plasma concentration
T max	Time to C max
C 24	Concentration at nominal time of 24 hours after dosing
C 168	Concentration at nominal time of 168 hours after dosing
CL/F	Apparent clearance
V/F	Apparent volume of distribution
T 1/2	Terminal half-life
AUC 0-inf	Area under the plasma concentration vs time curve from time zero hours to infinity
%AUC extrap	Percentage of AUC 0-inf extrapolated from T last to infinity
AUC 0-24	Area under the plasma concentration time curve from time of first dose to 24 hours after dosing
AUC 0-168	Area under the plasma concentration time curve from time of first dose to 168 hours after dosing

Note: Additional Parameters may be included as required

### **Summaries of PK concentration values and PK parameters**

All pharmacokinetic analyses will be performed on the Pharmacokinetic Analysis Set. For the End of Study analysis, the following apply:

Pharmacokinetic concentrations collected within the PK analysis visit window (see Section 6.3.3) will be summarised at every scheduled time point using descriptive statistics. PK concentrations sampled outside the PK sampling windows will be included in listings and in subject level figures but will not be included in data summaries.

Derived PK parameters will be summarised using descriptive statistics and stratified by dose and frequency.

PK concentrations derived after discontinuation of study treatment will be excluded from PK data summaries, in accordance with the 'while on-treatment' strategy for IE.

If a participant takes an incorrect dose or misses a dose, PK concentrations and PK parameters inferred until the next dose (in case more than one dose is administered during the study intervention period) or until the end of study intervention period (if there is only one dose or if incorrect dose is the last one) may be excluded from PK data summaries, as instructed by CPMS prior to final database lock.

The following figures will be produced:

- A by-participant graph of concentration data over time, stratified by cohort, on linear and semi-logarithmic scales
- Graph of arithmetic mean of concentration data over time, stratified by cohort, on linear and semi-logarithmic scales

Listings of PK concentration and PK parameter values will be produced.

#### **4.4. Exploratory Endpoint(s) Analyses**

##### **4.4.1. Adverse Events analyses**

Analyses described in Section [4.3.1.2](#) will repeated up to and including day 25.

##### **4.4.2. Liver panel laboratory analyses**

Change from baseline values for liver panel laboratory parameters will be summarised by visit. Visits up to Day 8 (inclusive) will exclude any liver panel values assessed under cART, if cART starts earlier for any reason.

Laboratory toxicities will be graded according to the DAIDS Criteria Version 2.1.

For liver panel lab tests that are gradable by DAIDS (e.g. ALT, AST), summary of worst-case grade increase from baseline grade will be provided. This summary will display the number and percentage of participants with a maximum post-baseline grade increase from their baseline grade (e.g. for participants with maximum increase from Baseline to grade 4 the number and percentage of them will be displayed, same for increase to grade 3, 2 and 1). Also, maximum increase subtotals (i.e. max increase in grade to any grade between 1 and 4, max increase to grade 2-4 or max increase to grade 3-4) will be included. The grade increases are determined by comparing the baseline grade to the worst-case post-baseline grade (e.g., Increase to Grade 1, Increase to Grade 2 etc.) and maximum grade increase subtotals (e.g., Increase to Grades 1 to 4, Increase to Grades 2 to 4, Increase to Grades 3 to 4). The grading subtotals are determined by adding the counts for each worst-case grade change within the subtotal category, e.g., ‘Increase to Grades 1 to 4’ is a subtotal of all worst-case increases to Grade 1, to Grade 2, to Grade 3, and to Grade 4. Participants with missing baseline value are to be assumed to have a Grade 0 at baseline. The determination of the worst case during the post-baseline period takes into account both planned and unscheduled assessments.

This summary will be produced while participants are under the monotherapy period, as well as overall (i.e. monotherapy and Follow-Up periods).

Liver panel data for participants with at least one abnormal lab value will be included in the listing of chemistry laboratory parameters. No imputation will be performed for missed assessments while participants are on study or after study withdrawal.

More details of all planned displays are provided in the OPS document.

#### **4.4.3. Immunology Analyses**

The immunology analyses will be performed using the Safety analysis set.

Change from baseline values for CD4 will be summarised at every assessment visit.

Visits up to Day 8 (inclusive) will exclude any values assessed under cART, if cART starts earlier for any reason, in line with the Estimand definition (Section 1.1.1).

#### **4.4.4. Virology Analyses**

Changes in the gag gene sequence from baseline through day 8 will be explored separately by the study virologist. These analyses will be performed after SAC, when the genotypic and phenotypic data become available.

### **4.5. Other Safety Analyses**

Other safety analyses will be based on the Safety Analysis Set, unless otherwise specified.

#### **4.5.1. Extent of Exposure**

If more than one study treatment dose is administered in the study intervention period (e.g. Part 1b) or if actual dosing data is available (i.e. drug accountability and whether each container includes active drug vs. placebo), summary of exposure will be provided and will include number and proportion of participants received one/two/more doses and/or summary of cumulative actual dose.

A listing of Exposure Data will also be created.

See OPS for further details.

#### **4.5.2. Additional Safety Assessments**

##### **Vital Signs**

Change from baseline values of vital signs (e.g. temperature, systolic and diastolic blood pressure, pulse rate etc.) will be summarized by assessment visit.

All vital signs data will be included in a listing.

**ECG**

If multiple ECG records are available for a visit/timepoint (e.g. in case of triplicate ECG), then the average for continuous ECG variables and the worst case for categorical will be used for data summaries for that visit/timepoint.

Change from baseline in continuous ECG parameters (e.g. heart rate, PR, QRS, QT, QTc intervals) will be summarized by assessment visit.

A summary of the number and percentage of participants with ECG findings will be summarized by assessment visit. The ECG findings to be summarized are the ECG interpretation and clinical significance (yes/no) of abnormal ECGs.

The number and percentage of participants with maximum QTc values (i.e., worst case) post-baseline relative to baseline will be summarized by ECG parameter (e.g., QTcF Interval, Aggregate), treatment, planned time, and category (the standard categories are: no change or post-baseline increase to  $\leq 450$  msec, any increase to  $> 450$  msec, increase  $> 450$  to  $\leq 480$  msec, increase  $> 480$  to  $\leq 500$  msec, and increase  $> 500$  msec). The maximum value category is determined by comparing the baseline value category to the worst-case post-baseline value category for each subject. The determination of the worst-case post-baseline considers both planned and unscheduled assessments.

Participants will be summarized (i.e. number of participants and percentage) by a categorization of their maximum increase in QTc value (e.g., QTcF Interval, Aggregate) (i.e., worst case) post-baseline relative to baseline. The standard categories for the worst-case shifts of QTc in msec are: Increase  $\leq 30$  msec, Increase of 31-60 msec, and Increase of  $> 60$  msec change from baseline in QTc interval. Participants with missing baseline values are excluded from the display.

These summaries will be produced while participants are under the monotherapy period, as well as overall (i.e. monotherapy and Follow-Up periods).

A figure plotting the baseline QTc and the worst-case post-baseline values will be produced. The figure will have reference lines at 450 and 500 msec for both the ordinate and the abscissa axes. There will be diagonal reference lines at equality (i.e. a 45-degree line), at equality plus 30 msec, and at equality plus 60 msec.

All ECG data will be included in a listing.

**Suicidality Score**

Baseline suicidality data assessed electronically via the C-SSRS questionnaire will be summarised. Number and percentage of participant with suicidal ideation or behaviour during lifetime and currently (i.e. within the past 2 months of screening) will be presented.

Post baseline (and baseline) participant-level suicidality data will be available via RAPIDO DV.

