| | 
Clinical prior MI:
 
 Two psychiatric SAEs in previous MI GSK3532795 clinical program (acute psychosis, homicidal/suicidal ideation) at supratherapeutic doses were seen in healthy participants in TQT study. Neuropsychiatric adverse events were reported infrequently in the GSK3640254 program and were mostly grade 1; Psychiatric SAEs have been reported in the Phase 2b studies, none were considered related and all cases had either baseline psychiatric history (not disclosed during screening) or confounded factors which were the most likely cause of the event. For the Phase 2b study evaluating GSK3640254/DTG relative to DTG/3TC, the rates of nervous system AESI were 9-23% relative to 10%, respectively. The psychiatric system AESI were 0-10% relative to 14%, respectively. For the Phase 2b study evaluating GSK3640254 relative to DTG (both in combination with 2 NRTI), the rates of nervous system AESI were 9-17% relative to 8%, respectively. The psychiatric system | 
arrange for urgent specialist psychiatric evaluation and management.
 
 Guidance for the management of emergent psychiatric symptoms are available (see Section 8). There are clinical stopping criteria based upon intensity of treatment-emergent psychiatric AEs (see Section 7). |

| Potential Risk of Clinical Significance | Summary of Data/Rationale for Risk | Mitigation Strategy |
|---|--|---|
| | AESI were 3-7% relative to 6%, respectively. | |

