8.3.6. Suicidal ideation and behavior risk monitoring

VH3739937 is not a central nervous system active drug nor is it being developed for a neurologic or psychiatric condition. However, given the risk of suicidal ideation at supratherapeutic doses identified in one study with another MI, GSK3532795, all participants will undergo assessment for suicidality in this study. Any clinically diagnosed case of suicidality (using the C-SSRS as tool during Screening, on-treatment, and in follow-up) will result in exclusion from the trial or (if already randomized) immediate discontinuation from the study. Moreover, in these cases, the Investigator will arrange for urgent psychiatric evaluation and management.

Participants with HIV infection occasionally may present with symptoms of depression and/or suicidality (suicidal ideation or behavior). In addition, there have been some reports of depression, suicidal ideation and behavior (particularly in patients with a pre-existing history of depression or psychiatric illness) in some patients being treated with other ARTs such as INSTIs, including DTG. Therefore, it is appropriate to monitor participants for suicidality before and during treatment.

Participants being treated with VH3739937 should be monitored appropriately and observed closely for SIB or any other unusual changes in behavior, especially at the beginning and end of the course of intervention, or at the time of dose changes, either increases or decreases. Participants who experience signs of SIB should undergo a risk assessment. All factors contributing to SIB should be evaluated and consideration should be given to discontinuation of the study intervention. It is recommended that the investigator consider mental health consultation or referral for participants who experience signs of suicidal ideation or behavior. Participants presenting with new onset/treatment emergent depression should be advised to contact the investigator immediately if symptoms of severe acute depression (including suicidal ideation/attempts) develop, because medical intervention and discontinuation of the study medication may be required.

When informed consent has been given, families and caregivers of participants being treated with VH3739937 should be alerted about the need to monitor participants for the emergence of unusual changes in behavior, as well as the emergence of SIB and to report such symptoms immediately to the study investigator.

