Baseline assessment of SIB and intervention-emergent suicidal ideation and behavior will be monitored during this study using the C-SSRS. The definitions of behavioral suicidal events used in this scale are based on those used in the Columbia Suicide History Form

[Posner, 2007]. Questions are asked on suicidal behavior, suicidal ideation, and intensity of ideation. Day 1 (Baseline) visit questions will be in relation to lifetime experiences and current experiences (within the past 2 months); all subsequent questioning is in relation to the last assessment. The C-SSRS is to be administered by a clinician at the timepoints specified in the SoA (Section 1.3). The C-SSRS will be conducted electronically by computer/tablet connected to the internet.

Additionally, the investigator will collect information using the PSRAE eCRF form in addition to the AE (non-serious or SAE) eCRF form on any participant that experiences a possible suicidality-related AE while participating in this study. This may include, but is not limited to, an event that involves suicidal ideation, a preparatory act toward imminent suicidal behavior, a suicide attempt, or a completed suicide. The investigator will exercise their medical and scientific judgment in deciding whether an event is possibly suicide-related. PSRAE forms should be completed and reported to GSK/ViiV Healthcare within 1 week of the investigator diagnosing a possible suicidality-related AE.

As described in Section 7.1.3, new onset suicidal ideation of concern to the Investigator (see below) at any time will result in immediate discontinuation from the study and the Investigator will arrange for urgent specialist psychiatric evaluation and management.

Emergent non-suicidal Psychiatric AE Evaluation and Management:

- Any Grade 1 or 2 Psychiatric AE: A Grade 1 or 2 Psychiatric AE may result in additional unscheduled visits (in-clinic or at home) as clinically indicated. This may include a more in-depth assessment of AE through interview, additional unscheduled clinical labs, and/or imaging. Psychiatric consultation may be required at the discretion of the Investigator. Any pharmacotherapy should be discussed with the Medical Monitor.

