9.3.3.1. Safety Analysis

All safety analyses will be performed on Safety Analysis set. Safety data will be presented in tabular format and summarized descriptively according to GSK's IDSL. No formal statistical analysis of the safety data will be conducted.

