#### 6.3.4. Multiple measurements at One Analysis Time Point

If ECG has been assessed more than once (e.g. in triplicate) at an analysis time point, the average of the available ECG measurements will be calculated and summary statistics will be based on the calculated average. This applies to both baseline and post baseline assessments.

For lab tests on a study day, if more than one assessment is taken on the same day, the test from a central lab will be taken over the test from a local lab. If multiple assessments are taken from the same type of lab on a study day, the worst case will be used.

Other Safety Endpoints
Columbia Suicide Severity Rating Scale (C-SSRS)

• Missing data will not have any imputation performed.

• A positive alert is triggered if a subject has reported suicidal ideation/behaviour in categories 4-9.

• Questions in categories 3-5 will be triggered if suicidal ideation is reported in categories 1 or/and 2.

• Incomplete calls:

○ when no complete call is databased on the same day, the data from the incomplete call will be used

Other Safety Endpoints	
Columbia Suicide Severity Rating Scale (C-SSRS)	
	
 
○ if a subject has only an incomplete call, and it resulted in a positive alert, the relevant pages in the CRF should be completed, even though the call was incomplete
 
○ when a complete call is databased on the same day, the data from the complete call will be used in the summaries.
 
● Duplicate calls, 
 
○ if they occur on the same day: 
 
■ Both calls will be reported in the listings.
 
■ For summary tables, the entry with latest time record will be used.
 
■ For summary tables at baseline, unscheduled repeat visits will not be summarised.
 
■ Relevant CRF pages will be completed based on the latest entry (if it was a positive alert).
 
 
 
○ If they occur on different days 
 
■ take the entry closest to the target visit date
 
 
 
 
 
● Visit 1 (Screening) assessments performed after study treatment initiation will not be included in Baseline summaries
 

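### The SAP specifies a C-SSRS results summary at baseline only, so post-dose C-SSRS findings reach a specified table only if they are recorded as adverse events

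*SAP*

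**What the plan says.** SAP 4.5.2, under Suicidality Score, commits to one C-SSRS results output: "Baseline suicidality data assessed electronically via the C-SSRS questionnaire will be summarised". It gives the number and percentage of participants with ideation or behaviour over their lifetime and currently, counted back from screening. For everything later the text is: "Post baseline (and baseline) participant-level suicidality data will be available via RAPIDO DV".

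Protocol 8.3.6 states what the scale is for: "Baseline assessment of SIB and intervention-emergent suicidal ideation and behavior will be monitored during this study using the C-SSRS". It also says why suicidality is assessed: "given the risk of suicidal ideation at supratherapeutic doses identified in one study with another MI, GSK3532795, all participants will undergo assessment for suicidality". On presentation, protocol 9.3.3.1 is general: "Safety data will be presented in tabular format and summarized descriptively according to GSK's IDSL".

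SAP 6.3.4 sets C-SSRS data rules. It defines a positive alert as a report in categories 4-9. For duplicate calls on the same day it says: "For summary tables, the entry with latest time record will be used". It then gives a separate rule for summary tables at baseline, and it says both duplicate calls go into the listings. SAP 6.2.1 reports C-SSRS completion for each cohort against a 90% target.

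**The concern.** A table of lifetime and pre-dose suicidality describes who was enrolled. It cannot show whether anything emerged on the drug. Under SAP 4.5.2 as written, a positive or worsened answer after dosing enters a specified table only if the investigator judges it to be an adverse event. The plan would then report whether the post-dose scales were completed, but not what they showed.

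The protocol gives a reason to look. Its risk table cites "Two psychiatric SAEs in previous MI GSK3532795 clinical program (acute psychosis, homicidal/suicidal ideation) at supratherapeutic doses". C-SSRS is also the exception within SAP 4.5.2: vital signs, ECG and laboratory data all get post-baseline summaries, and ECG and laboratory data also get worst-case displays for monotherapy and overall.

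**Working it through.** The plan states no figure to reproduce. The check is a comparison of texts, followed by a count of what is affected.

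**Outputs that the SAP specifies**

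| Source of information | Before dosing | After dosing |
|---|---|---|
| C-SSRS results (SAP 4.5.2) | Number and percentage | Participant-level data in the viewer |
| C-SSRS completion (SAP 6.2.1) | By cohort, all assessments together | By cohort, all assessments together |
| Positive alert, categories 4-9 (SAP 6.3.4) | Defined; no output named | Defined; no output named |
| Possible suicidality-related AE (PSRAE) form (protocol 8.3.6) | Not applicable | No display named |
| Suicidality recorded as an AE (SAP 4.1.1, 4.3.1.2, 4.4.1) | Not applicable | Tabulated by dose and placebo, repeated through Day 25; all AEs listed |

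Only the last row brings post-dose suicidality into a specified table. It depends on investigator judgement: protocol 8.3.6 leaves it to the investigator to decide whether an event may be suicide-related, and the stopping criterion in protocol 7.1.3 requires a clinical diagnosis.

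**Count**

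- Participants (SAP 1.2): 20 in Part 1 + 7 in Part 2 = 27. Active: 18 + 6 = 24. Placebo: 2 + 1 = 3.
- Scheduled C-SSRS (protocol 1.3): Screening plus two after dosing, Day 7 and Day 25 as the columns read = 3 each.
- All scheduled: 27 × 3 = 81. After dosing: 27 × 2 = 54. Share: 54/81 = 66.7%.
- Of the 54, 27 are Day 25 assessments, about 25 − 8 = 17 days after the planned start of cART. The other 27 fall in the monotherapy period.

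**What a table could show**

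With zero events among n participants, the one-sided 95% upper limit is 1 − 0.05^(1/n):

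- one active cohort, n = 6: 1 − 0.05^(1/6) = 39.3%
- all active, n = 24: 1 − 0.05^(1/24) = 11.7%
- placebo, n = 3: 1 − 0.05^(1/3) = 63.2%

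The chance of at least one event in a cohort of 6 is 1 − (1 − p)^6. The documents give no rate, so p is assumed: 26.5% at p = 5%, 46.9% at 10% and 73.8% at 20%. The table would let a reader see whether anything occurred. It could not rank cohorts.

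**The case against.** The strongest reply is that suicidality is reported, by another route. Protocol 8.3.6 sends any possible suicidality-related AE, expressly including ideation, to the AE form as well as the PSRAE form. The SAP tabulates AEs by maximum grade, SAEs and AEs leading to discontinuation, by dose and placebo, and lists all AEs. The grading table in protocol 10.8 places suicidal ideation or attempt at Grade 4, and clinically diagnosed new-onset ideation is a stopping criterion. SAP 6.3.4 also requires the relevant CRF pages to be completed after a positive alert, and a clinician administers the scale. All of this stands. A reader might infer that treatment-emergent suicidality goes unreported by cohort; the documents do not support that.

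A reader might also infer that every post-dose result stays in the viewer. That cannot be shown. SAP 6.3.4 mentions C-SSRS listings, and SAP 4.1.1 leaves the choice of static listings to the OPS, which was not available. The SAP is ambiguous here rather than silent.

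Third, the stakes are limited. C-SSRS is not an endpoint, no formal safety analysis is planned, and the scale also serves eligibility and individual discontinuation. Protocol 2.3 calls neuropsychiatric safety a potential risk, and 2.3.1 reports no psychiatric AEs with VH3739937, so calling this a known harm of the drug would go too far. Half of the post-dose assessments fall under cART, and protocol 8.3.6 itself notes reports of suicidality with other antiretrovirals.

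These points reduce the size of the gap but do not close it. SAP 6.3.4 does not say which CRF pages follow an alert, and answers below the alert threshold need not become AEs. An unseen OPS cannot be assumed to hold a table that SAP 4.5.2 does not call for.

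**Conclusion.** The gap is real and moderate. SAP 4.5.2 specifies C-SSRS results at baseline only, which does not fit the monitoring purpose in protocol 8.3.6, the tabular presentation in protocol 9.3.3.1 or the data rules in SAP 6.3.4. What is lost is the C-SSRS-based result after dosing, mainly positive or worsened answers that the investigator does not record as AEs. Events that are recorded as AEs, SAEs or discontinuations remain visible by dose.

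The 67% counts scheduled assessments without a specified results summary; it does not measure harm missed. It assumes full enrolment of 27 and the schedule as its columns read. The conclusion also assumes that the OPS adds no post-baseline C-SSRS table. If it does, only the mismatch between SAP 4.5.2 and 6.3.4 remains. The primary analysis is unaffected.

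**What to change.** Before database lock, amend SAP 4.5.2 as follows.

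- Add one descriptive table by cohort, with placebo pooled: number and percentage of participants with any post-baseline C-SSRS ideation, any behaviour and any positive alert (categories 4-9). Mark those that are new or worse than the pre-dose value. Show it for monotherapy and overall.
- Name the pre-dose reference. Protocol 8.3.6 speaks of a Day 1 baseline, while the schedule places the pre-dose C-SSRS at Screening.
- Add one static listing of positive post-baseline C-SSRS records and PSRAE records.
- Align SAP 4.5.2 with 6.3.4, so that the alert definition and the summary-table rules each belong to a named output.

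The cost is SAP wording, one table and one listing, all from data already collected. No visit, procedure or clinical rule changes. The downside is that both outputs are descriptive only, and the Day 25 results should be labelled as obtained under cART.
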